### 10.15.5 Time to First Pain-Free Timepoint

For NRS scores for pain, subjects achieving no migraine headache pain timepoints will be flagged for each subject within each study period. The first pain-free timepoint in which the no migraine (score 0 or 1) achieved will be considered as the time to first pain-free timepoint. Time to first pain-free timepoint will be calculated based on the actual time difference as below.

Time (hours) = (Time the corresponding timepoint recorded - Time IMP was taken) / 60.

Subjects who did not achieve no migraine at 24 hours will be censored at 24 hours.

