10.4 Exploratory endpoints

1. The percentage of subjects who are "sustained pain-free," defined as having no migraine headache pain at 24 hours, with no use of rescue medication and no relapse of headache pain within 24 hours (24-hour sustained pain-free) after administration
2. The time to first pain-free timepoint following treatment with oral LAT8881 compared with placebo to 24 hours post dose, with no use of rescue medication
3. Supplemental analgesic medication use in the 24 hour post treatment period
4. Subject satisfaction with each treatment based on a 7-point Likert Scale, overall preference for Treatment 1 or Treatment 2, and historical comparison with usual treatment
5. Association between change in headache pain and symptom scores and selected subject baseline characteristics, including for example, migraine with/without aura, relationship to menstrual cycle

11. Study measurements

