#### 3.3 Exploratory Objectives

- 1. To investigate the percentage of subjects who are “sustained pain-free,” defined as having no headache pain following treatment with oral LAT8881 for a migraine headache compared with placebo, with no use of rescue medication and no relapse of headache pain within 24 hours (24-hour sustained pain-free) after administration*
- 2. To investigate the time to first pain-free timepoint following treatment with oral LAT8881 for a migraine headache compared with placebo to 24 hours post dose, with no use of rescue medication*
- 3. To determine the need for extra analgesic (rescue) medication after treatment with oral LAT8881 administration for a migraine headache, compared with placebo*
- 4. To investigate subject satisfaction with treatment of a migraine headache*
- 5. To investigate other factors influencing the extent of change in pain score and symptom scores in subjects with migraine headaches*

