### 7.4 Exploratory Endpoints

- 1. The percentage of subjects who are "sustained pain-free," defined as having no migraine headache pain at 24 hours, with no use of rescue medication and no relapse of headache pain within 24 hours (24-hour sustained pain-free) after administration*
- 2. The time to first pain-free timepoint following treatment with oral LAT8881 compared with placebo to 24 hours post dose, with no use of rescue medication*
- 3. Supplemental analgesic medication use in the 24 hour post treatment period*
- 4. Subject satisfaction with each treatment based on a 7-point Likert Scale, overall preference for Treatment 1 or Treatment 2, and historical comparison with usual treatment*

5. *Association between change in headache pain and symptom scores and selected subject baseline characteristics, including for example, migraine with/without aura, relationship to menstrual cycle*

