## 9.2 Per Protocol (PP) Population

The Per Protocol (PP) population will include all subjects who received at least one dose of IMP and excludes subjects who have any major protocol deviation impacting the study endpoints. Deviations

for exclusion from the PP population due to inadequate exposure to IMP or completeness of primary efficacy endpoint will be determined during the blinded review meeting prior to database lock.

*A per-protocol (PP) population will be used for efficacy analyses and to analyse exploratory endpoints.*

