## 10.16 Paired Difference in Pain-Free Subjects

Difference between treatments (LAT8881 – Placebo) for No Headache Pain at each timepoint, Sustained Pain-Free at 24 hours and First Pain-Free Timepoint will be calculated as below for the percentage difference; the numerator represents the difference in the number of subjects.

	Placebo		Total
	Pain free	Pain	
LAT8881			
Pain free	a	b	a + b
Pain	c	d	c + d

Total	a + c	B + d	a + b + c + d
-------	-------	-------	---------------

$$\text{Pain free for placebo (\%)} = \frac{a + c}{a + b + c + d}$$

$$\text{Pain free for LAT8881 (\%)} = \frac{a + b}{a + b + c + d}$$

$$\text{Pain free (LAT8881 - Placebo) (\%)} = \frac{a + b}{a + c + b + d} - \frac{a + c}{a + b + c + d} = \frac{b - c}{a + b + c + d}$$

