#### 11.8.3.2 Time to First Pain-free Timepoint

The number and percentage of subjects with their first pain free timepoint will be presented by timepoint. The paired difference in the number of subjects with their first pain free timepoint will be calculated as mentioned in section 10.16.

Time taken to first pain-free timepoint will also be analysed using Kaplan-Meier curve. Time to first pain-free timepoint will be calculated based on the actual time taken from IMP as mentioned in section 10.15.5.

In DDP: Table 14.2.6.1, Figure 14.2.6.2

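### Time to first pain-free counts relief after rescue as success, although the endpoint requires no rescue; the secondary pain-free objective and endpoint also disagree on this condition

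*SAP*

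**What the plan says.** **Time to first pain-free timepoint.** The rescue-free condition appears wherever this endpoint is defined:

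- Protocol 10.4, exploratory endpoint 2: "following treatment with oral LAT8881 compared with placebo to 24 hours post dose, with no use of rescue medication".
- SAP 7.4 repeats it: "compared with placebo to 24 hours post dose, with no use of rescue medication".
- The matching objective in SAP 3.3 has it too: "for a migraine headache compared with placebo to 24 hours post dose, with no use of rescue medication".

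SAP 10.15.5 then gives one event rule, "The first pain-free timepoint in which the no migraine (score 0 or 1) achieved will be considered as the time to first pain-free timepoint", and one censoring rule, "Subjects who did not achieve no migraine at 24 hours will be censored at 24 hours". Neither mentions rescue. SAP 11.8.3.2 says the Kaplan-Meier time is "calculated based on the actual time taken from IMP as mentioned in section 10.15.5".

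**Secondary pain-free rates.** Secondary objective 2 (Protocol synopsis, Protocol 4.2, SAP 3.2) concerns freedom from headache pain up to 8 h without rescue. Secondary endpoint 3 (Protocol synopsis, Protocol 10.2, SAP 7.2) lists the percentages at six timepoints without that condition. Protocol 14.5, SAP 10.15.4 and SAP 11.8.2.5 follow the endpoint: a score of 0 or 1 is enough.

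**Rescue.** SAP 4.1 and Protocol 8.2.3 allow rescue from 2 h after the dose.

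**The concern.** A subject may get no benefit from the dose, take rescue after 2 h and score 0 at 4 h. Under 10.15.5 that subject enters the Kaplan-Meier curve and the first-pain-free table as a success. The output then measures the dose plus whatever was taken afterwards, which is not what exploratory objective 2 asks. The 4 h and 8 h pain-free percentages fall short of secondary objective 2 for the same reason.

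If any rescued subject later scores 0 or 1, that treatment's rate is higher than its rescue-free rate. The treatment difference is distorted when this rescue relief differs between treatments. A drug that works should leave fewer subjects needing rescue, so placebo would gain more of these events and the drug's benefit would be understated.

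**Working it through.** **1. Does any section supply the missing condition?**

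- SAP 10.16 applies its two-way table "for No Headache Pain at each timepoint, Sustained Pain-Free at 24 hours and First Pain-Free Timepoint will be calculated as below"; the formula has no rescue term.
- SAP 11.8.3.2 only points back to 10.15.5.
- SAP 10.15.3 sends timing deviations to blinded review, not rescue.
- SAP 9.2 "excludes subjects who have any major protocol deviation impacting the study endpoints". Rescue that the protocol permits is not, as such, a deviation.
- SAP 10.15.2, the sustained pain-free flag, does contain the condition. It is the only pain-free derivation that does.

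Nothing supplies it for 10.15.5.

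**2. Which scores are exposed?** With rescue from 2 h, the exposed scores are those at 4, 8 and 24 h (3 of 7) for the exploratory endpoint and at 4 and 8 h (2 of 6) for the secondary one. Scores to 2 h are clean if the 2 h rule is kept and the 2 h score is not recorded late.

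**3. What is one subject worth?** The plan states no response or rescue rates. Its only relevant figure is 20 completers: 20/(1 − 0.20) = 25 against 26 enrolled, and 26 × 0.80 = 20.8. With 20 pairs, one reclassified subject moves a rate by 1/20 = 5 points.

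**4. How large could the effect be?** All inputs here are assumptions. Let p be the true rescue-free rate (40% LAT8881, 20% placebo), u the share of all subjects who take rescue without an earlier pain-free score, and s the share of those who are pain-free afterwards.

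Reported rate = p + u·s

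Reported difference = 20 − s·(u placebo − u LAT8881) points

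In the equal-rescue-rate rows, u = (1 − p)·r, where r is one rescue rate among subjects not otherwise pain-free.

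| Scenario | u, LAT8881 v placebo | s | Reported rates | Difference |
|---|---|---|---|---|
| Equal share of all subjects rescued | 30% v 30% | 0.5 | 55% v 35% | 20.0 |
| Equal rate, r = 0.3 | 18% v 24% | 0.4 | 47.2% v 29.6% | 17.6 |
| Equal rate, r = 0.5 | 30% v 40% | 0.5 | 55% v 40% | 15.0 |
| Equal rate, r = 0.7 | 42% v 56% | 0.7 | 69.4% v 59.2% | 10.2 |
| r = 0.4 v 0.6 | 24% v 48% | 0.5 | 52% v 44% | 8.0 |
| r = 0.3 v 0.7 (extreme) | 18% v 56% | 0.5 | 49% v 48% | 1.0 |

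In 20 completers the r = 0.5 row is 11 v 8 subjects instead of 8 v 4. Erasing the 20 points needs a rescue gap of 20/s: 40 points at s = 0.5, or 28.6 at s = 0.7. With no true effect, a 10-point rescue gap at s = 0.5 creates a 5-point difference, one subject in 20.

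**5. A second model, followed to 24 h.** Assume 20% v 10% pain-free by 2 h. Of the rest, 20–60% on LAT8881 and 40–80% on placebo take rescue (LAT8881 never higher). Pain-free by 24 h are 50–80% of those rescued and 40% of those not rescued. The 24 h difference is −16.4 to +5.6 points as the SAP is written, and +7.6 to +28.4 if a score after rescue is not an event. The written rule gave the smaller difference in every combination tried, and a reversed sign in some.

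**6. Why not censor at rescue?** Take 20 per treatment, rescue in 6 v 8 subjects between 2 h and 4 h, and 8 v 4 rescue-free events at 4 h. Censoring at rescue gives 8/14 = 57% v 4/12 = 33%. Holding rescued subjects as not achieved gives 8/20 = 40% v 4/20 = 20%.

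**The case against.** The strongest reply is that 10.15.5 is silent rather than wrong. It never says that scores after rescue count, it sits under an endpoint that states the condition, and the Data Display Plan cited in SAP 12 has not been seen. But a programmer following 10.15.5 would count those scores, and 10.15.2 shows that the SAP writes the condition into a derivation when it means to apply it.

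Several narrower points stand:

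- Protocol 14.5 also describes the first-pain-free table and curve without a rescue rule, so the gap is not only in the SAP.
- Protocol 8.2.1 lists NSAIDs as prohibited throughout the study, under a prophylaxis heading, while 8.2.3 permits standard-of-care rescue. Whether NSAID rescue is a deviation is therefore unsettled, and those passages must be reconciled.
- Secondary objective 2 speaks of any timepoint to 8 h, whereas endpoint 3 gives a rate at each timepoint. That is a second mismatch.
- Read against endpoint 3 alone, the 4 h and 8 h rates are what was specified; they fall short only against the objective.
- The outputs are descriptive, no test of them is planned, and SAP 11.6 tabulates and lists rescue use. A reader can see the exposure, but the derivations stay uncorrected.
- The sizes above rest wholly on assumed rates, and one scenario shows no distortion.

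**Conclusion.** The concern holds. As written, SAP 10.15.5 does not deliver exploratory endpoint 2, because relief after rescue counts as an event at 4, 8 and 24 h. The conflict between secondary objective 2 and endpoint 3 is also real, but it begins in the protocol and SAP 10.15.4 carries it forward.

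Neither the direction nor the size can be fixed from the documents. Under the assumed 40% v 20%, the reported difference runs from 20 points (equal share of all subjects rescued, equal relief) through 15 to 1. The understatement arises when more placebo subjects than LAT8881 subjects take rescue.

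The effect is confined to secondary and exploratory descriptive results. The primary mixed model (SAP 11.8.1.3) analyses change in pain score and does not use these derivations, although it states no rescue rule of its own. The point should be corrected before unblinding.

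**What to change.** - **SAP 10.15.5.** Count an event only if no rescue was taken between the dose and that score. Carry rescue users without an earlier event as not achieved, censored at 24 h rather than at the rescue time.
- **State the reading of the condition.** Either (a) no rescue before the pain-free score, or (b) no rescue in the whole 24 h. The endpoint wording can bear both. I suggest (a): under (b) an event at 1 h depends on what happens later, and 10.15.2 already covers the whole window. The choice matters. If 25% of subjects who were pain-free before any rescue take it later, (a) gives 40% v 20% and (b) gives 30% v 15%.
- **Secondary endpoint.** Reconcile objective 2 with endpoint 3, Protocol 14.5 and SAP 10.15.4, including the any-timepoint wording. I suggest adding the condition to the endpoint: the objective has it in all three places, and endpoint 3 is the only pain-free endpoint without it. SAP 10.15.4 would then class a subject as not pain-free at every timepoint after rescue, with score-only rates kept as a labelled supportive table.
- **Unclear order.** Add a rule for the blinded review that an unclear order counts as rescue before the score. SAP 10.9 only places medication before or after the study dose.

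**Cost.** This needs SAP text, derivation code and matching of rescue to actual score times. The migraine diary collects concomitant medications alongside the scores (Protocol 9.3), but confirm that it records clock times. Editing endpoint 3 is a protocol amendment, so the ethics committee must be informed (Protocol 15.1.4). Reported rates from 4 h will fall if rescued subjects became pain-free: in the r = 0.5 scenario, from 55% to 40% on LAT8881 and from 40% to 20% on placebo. The unclear-order rule may lower them further. No clinical rescue rule changes.

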### 10.3 Visits

Analysis visits will be defined as follows:

Visit as per CRF	Study Period	Analysis Visit
Visit 1 (Days -28 to -1)	-	Visit 1 (Screening)
Day 1, Visit 2	Period 1	Visit 2
Day 15, Telephone Visit 1	Period 1	-
Day 29, Visit 3	Period 1	Visit 3
Day 44, Telephone Visit 2	Period 2	-
Day 57, Visit 4	Period 2	Visit 4
Day 64, Visit 5 or Early Termination	Period 2	Visit 5 (End of Study)

Analysis timepoints for efficacy endpoints within each study period will be defined as follows:

Timepoint as per CRF	Analysis Timepoint
Before IMP was taken (Pre-dose)	Pre-dose
30 minutes after IMP taken (t=0.5 hrs)	30 minutes
1 hour after IMP taken (t=1 hr)	1 hour
1.5 hours after IMP taken (t=1.5 hrs)	1.5 hours
2 hours after IMP taken (t=2 hrs)	2 hours
4 hours after IMP taken (t=4 hrs)	4 hours
8 hours after IMP taken (t=8 hrs)	8 hours
24 hours after IMP taken (t=24 hrs)	24 hours

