### 10.15.3 Time Deviated from Scheduled Timepoints

Actual time difference from ‘Time IMP was taken’ to each of the timepoints will be calculated and discussed during blinded review meeting and any analysis flags may be created to exclude the same.

Time deviated (hours) = (Time the corresponding timepoint recorded - Time IMP was taken) / 60.

Time difference between pre-dose measurement and IMP dosing should not be more than 30 mins. This difference will also be highlighted in the blinded review meeting.

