### 10.15.4 Responder

Subjects achieving no migraine headache pain at each time point in each study period will be separately flagged for analysis. Presence or absence of pain will be determined as follows:

- Absence: NRS Pain score 0 or 1 at the corresponding timepoint.
- Presence: NRS Pain score more than 1 at the corresponding timepoint.

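### Time to first pain-free: events use actual diary times but non-responders are censored at exactly 24 h, so one late 24-hour response forces the Kaplan-Meier curve to 100%

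*SAP*

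**What the plan says.** SAP 10.15.4 defines the event: "Absence: NRS Pain score 0 or 1 at the corresponding timepoint". SAP 10.15.5 then times the first such entry by the clock ("Time to first pain-free timepoint will be calculated based on the actual time difference as below"), with the formula "Time (hours) = (Time the corresponding timepoint recorded - Time IMP was taken) / 60" and no upper limit. For everyone else it says "Subjects who did not achieve no migraine at 24 hours will be censored at 24 hours".

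SAP 11.8.3.2 repeats the actual-time rule ("Time to first pain-free timepoint will be calculated based on the actual time taken from IMP as mentioned in section 10.15.5") and states the display: "Time taken to first pain-free timepoint will also be analysed using Kaplan-Meier curve". The same section tabulates subjects by first pain-free timepoint, which means by scheduled slot.

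SAP 10.3 lists the 24-hour slot without a window. SAP 10.15.3 has actual deviations from schedule calculated for each timepoint, to be "discussed during blinded review meeting and any analysis flags may be created to exclude the same". The only limit it states is 30 minutes for the pre-dose measurement. Protocol 14.5 asks for the Kaplan-Meier curves without giving a time rule.

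**The concern.** Events and censorings are on two different clocks. An event can fall after 24.0 h, because the diary entry may be late. A censoring cannot. Past 24.0 h the risk set therefore holds only subjects whose 24-hour response was recorded late, and the estimate must fall to zero as they have their events.

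The end of each curve then depends on how punctual the 24-hour entries were rather than on how many subjects became pain-free. Two treatments with the same response can show different curves at the end of follow-up, and a real difference can be hidden. The curve is the only time-to-event display for the second exploratory objective, so a reader would look there for the timing of relief.

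This arises in subjects with complete diaries. It is not a question of diaries that stop early.

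**Working it through.** The documents give no numerical result for this endpoint, so there is no stated figure to reproduce. The check applies the SAP's rules to assumed data.

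**Inputs from the documents.** Event at the first score of 0 or 1; event time is actual elapsed hours, uncapped; non-responders censored at 24.0 h (SAP 10.15.4 and 10.15.5). The sample size of 20 per curve is the planned number of completers, each of whom contributes to both curves (SAP 4.2).

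**Formula.** S(t) is the product of (1 − d/n) over event times up to t, where d is the number of events and n the number at risk. The proportion pain-free is 1 − S(t).

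**General result.** All non-responders leave at 24.0 h. At the last event time after 24.0 h everyone still at risk has the event, so d = n, the factor is 0 and 1 − S = 100%. This holds for any sample size and any number of non-responders.

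**Illustration (assumed counts).** Of 20 subjects, 8 are pain-free by 8 h, 6 more at the 24-hour entry and 6 never. The observed proportion is 14/20 = 70%.

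*One late entry.* Five of the six record at 23.5 to 23.9 h and one at 24.1 h.
- At 24.0 h: 13/20 = 65% pain-free; six are then censored.
- At 24.1 h: n = 1, d = 1, so S = 0.35 × 0 = 0 and the curve reads 100%.

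*Four late entries.* Two record at 23.8 and 23.9 h, four at 24.1, 24.2, 24.3 and 24.5 h. At 24.0 h, 10/20 = 50% are pain-free and six are censored. Then:

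| Time (h) | At risk | S | Pain-free |
|---|---|---|---|
| 24.1 | 4 | 0.5 × 3/4 = 0.375 | 62.5% |
| 24.2 | 3 | 0.375 × 2/3 = 0.25 | 75% |
| 24.3 | 2 | 0.25 × 1/2 = 0.125 | 87.5% |
| 24.5 | 1 | 0.125 × 0 = 0 | 100% |

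If the plot were cut at 24.0 h, these two cases would read 65% and 50% against 70%. A comparison curve with the same response and all entries on time would read 70%, so delay alone would create a gap of 5 or 20 percentage points.

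**Other response levels.** One late first response at 24.25 h, 20 subjects:

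| Earlier responders | Curve at 24.0 h | Curve at 24.25 h | Observed | Median under SAP rule | Median on one clock |
|---|---|---|---|---|---|
| 4 | 20% | 100% | 5/20 = 25% | 24.25 h | not reached |
| 8 | 40% | 100% | 9/20 = 45% | 24.25 h | not reached |
| 11 | 55% | 100% | 12/20 = 60% | unchanged | unchanged |

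Moving that entry to 23.9 h or exactly 24.0 h gives 25%, 45% and 60%.

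**How likely (assumed range).** Let q be the chance that a subject is first pain-free at the 24-hour slot and p the chance that such an entry is late. The chance of at least one such entry per curve is 1 − (1 − qp)^20. For q = 5% and p = 25% it is 1 − 0.9875^20 = 22%. For q = 30% and p = 50% it is 1 − 0.85^20 = 96%.

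**The case against.** The strongest objection is that the censoring sentence is open to another reading. SAP 10.3 uses 24 hours as the label of an assessment, so censoring there could mean at the actual time of that entry. On that reading the distortion shrinks: with assumed entry times 0.1 h apart from 23.8 h, the three cases in the second table end at about 27%, 49% and 66% instead of 100%. That much stands. But the SAP does not say it, and it is not a full cure. The curve still ends at 100% whenever the latest entry for that treatment belongs to a responder. With six responders and six non-responders at that slot, and punctuality unrelated to outcome, the chance of that is 6/12 = 50%.

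Second, the endpoint in SAP 7.4 runs only to 24 hours, so the jump lies outside its horizon. True, but no truncation of the plot is specified, and stopping there drops responders whose entry was late.

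Third, blinded review looks at timing deviations. The flags are optional, no window is set for post-dose entries, and excluding a late entry discards a real response.

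Fourth, the table in SAP 11.8.3.2 gives the right proportion. It does, and it could then show 70% beside a figure from the same data that ends at 100%.

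Finally, the setting is narrow: the late entry must be the subject's first pain-free score, the endpoint is exploratory, and the documents say nothing about how often entries are late. These points limit the importance of the defect but do not remove it.

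**Conclusion.** The concern holds: the rule is wrong as written. With uncapped actual event times and censoring at exactly 24.0 h, any first pain-free entry after 24.0 h takes that treatment's curve to 100%. This follows from the estimator and needs no assumption about sample size or response rate. The illustrated sizes (65% then 100%, or 50% then 100%, against 70%) and the 22% to 96% chance per curve rest on assumed counts and assumed punctuality.

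Up to 24.0 h the curve correctly reflects entries made by then. The damage is the jump afterwards, a false median just above 24 h when fewer than half were pain-free before, and an understated proportion if the plot is stopped at 24.0 h. It should be corrected before database lock, but it affects one exploratory figure and no planned test.

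**What to change.** In SAP 10.15.5 and 11.8.3.2, state that the time to first pain-free is the scheduled timepoint (0.5, 1, 1.5, 2, 4, 8 or 24 h) for events, that non-responders are censored at the scheduled 24 h, and that events precede censorings at that time. Keep the actual times in the listings.

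In both illustrated cases the curve then ends at 70% and agrees with the table. With one late entry, S = 0.35 × 6/7 = 0.30; with four, S = 0.50 × 6/10 = 0.30. (For simplicity these sums move only the late entries to 24 h. Placing all six there gives 0.60 × 6/12 = 0.30.)

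If the sponsor prefers actual times, capping late 24-hour entries at 24 h under the same tie rule also cures the tail.

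The cost is one sentence and a simpler derivation. Scheduled times lose resolution in minutes, which seven assessments over 24 hours do not support, and they place a markedly late earlier entry at its nominal slot. The listing keeps such entries visible.

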14.1 General considerations

The statistical analysis principles described below will be supplemented by a comprehensive statistical analysis plan (SAP) which will be finalised before the database is locked. This will contain details of methods for handling missing data, early withdrawals, data derivations and presentation. Any changes to the statistical analysis plan will be described and justified in the final report.

The descriptive summary for the categorical variables will include counts and percentages. The descriptive summary for the continuous variables will include number of subjects (n), means, medians, standard deviations, and minimum and maximum values. All data will be listed for all subjects. Treatment period order will be ignored in any treatment comparisons. Results will be presented in a descriptive format by treatment within each treatment period and overall. Treatment comparisons will take into account the paired nature of the treatment responses where feasible. As this is a Phase IIa proof of concept study, no formal statistical hypotheses are being specified although some may be investigated as part of the data presentation, in which case corresponding 95% confidence intervals will be presented and p-values of <0.05 will be declared statistically significant.

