## 7 Efficacy and Safety Endpoints

### 7.1 Primary Efficacy Endpoints

*Change in migraine headache pain score, using an 11-point NRS, (0 = none, 10 = worst imaginable), from the time of dosing to 0.5, 1.0, 1.5, 2, 4, 8 and 24 hours post dose. Pain is recorded in a subject diary and should reflect the subject's pain at the time of recording.*

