## 8.2 Handling Missing/Incomplete Data

Partial dates will not be imputed.

Flags identifying the study period for the start/stop dates for prior/ concomitant medications and adverse events will be generated (see Sections 10.9 and 10.10).

The method for missing data imputation for the primary endpoint will be discussed during the blinded review meeting prior to database lock.

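### Time to first pain-free: the fixed 24 h censoring rule has no exception for a diary that ends early, so the Kaplan-Meier curve treats unobserved hours as observed pain

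*SAP*

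**What the plan says.** SAP 7.4 defines the endpoint as time to the first pain-free timepoint, "compared with placebo to 24 hours post dose, with no use of rescue medication". SAP 10.15.5 takes the first NRS score of 0 or 1 as the event and dates it by the clock: "Time to first pain-free timepoint will be calculated based on the actual time difference as below". Its only censoring rule is "Subjects who did not achieve no migraine at 24 hours will be censored at 24 hours". SAP 11.8.3.2 then states: "Time taken to first pain-free timepoint will also be analysed using Kaplan-Meier curve". No test, hazard ratio or other effect measure is planned for the curve.

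The scores come from the diary that also serves the primary endpoint, "from the time of dosing to 0.5, 1.0, 1.5, 2, 4, 8 and 24 hours post dose".

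Protocol 14.1 left missing data to the SAP: "This will contain details of methods for handling missing data, early withdrawals, data derivations and presentation". SAP 8.2 defers the matter, and for the primary endpoint only: "The method for missing data imputation for the primary endpoint will be discussed during the blinded review meeting prior to database lock". SAP 9.2 similarly leaves open which per-protocol exclusions for inadequate exposure or "completeness of primary efficacy endpoint will be determined during the blinded review meeting prior to database lock". SAP 10.15.3 allows flags for entries made off schedule. None of these sets a censoring time for this endpoint.

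**The concern.** A Kaplan-Meier estimate assumes that each subject was observed without the event up to the time assigned as censoring. A subject whose diary ends at 4 h was not observed at 8 h or 24 h. Censoring that subject at 24 h keeps them in both later risk sets as a known non-event.

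The entries are self-recorded during a migraine, and after the 2 h entry the gaps are 2, 4 and 16 hours. Some incomplete diaries are therefore plausible, although the documents give no completion rate. The pain-free proportion, the median and the visual comparison of the two treatments are at stake. If completion differs by treatment, part of any separation between the curves would reflect diary-keeping.

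There is a related gap. The endpoint requires no rescue medication, but the derivation in 10.15.5 does not say what happens to a score of 0 or 1 recorded after rescue.

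**Working it through.** The plan gives no figure for this endpoint to reproduce: no expected pain-free rate and no diary-stop rate. The numbers below illustrate the mechanism under stated assumptions.

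**From the documents:** seven post-dose entries (SAP 7.1); event at the first score of 0 or 1, otherwise censored at 24 h (SAP 10.15.5); 20 planned completers (SAP 4.2).

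**Assumed:** true cumulative pain-free F(t) of 2, 5, 10, 20, 35, 50 and 70% at 0.5, 1, 1.5, 2, 4, 8 and 24 h. A fraction m of diaries stops after entry s, independently of pain.

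**Step 1, the SAP rule.** Nobody leaves the risk set before 24 h except by an event, so the estimate is observed events divided by all subjects:

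estimate at 24 h = F(s) + (1 − m) × [F(24) − F(s)], so bias = −m × [F(24) − F(s)].

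With s = 2 h this is 20 + (1 − m) × 50:

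| Diaries stopped | SAP rule | Last-score censoring |
|---|---|---|
| 0% | 70.0% | 70.0% |
| 5% | 67.5% | 70.0% |
| 10% | 65.0% | 70.0% |
| 20% | 60.0% | 70.0% |
| 30% | 55.0% | 70.0% |

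**Step 2, last-score censoring.** Stopping shrinks events and risk set by the same factor (1 − m), which cancels: S(24) = 0.80 × (0.65/0.80) × (0.50/0.65) × (0.30/0.50) = 0.30, so 70% pain-free for any m below 1. A simulation with 20 subjects per treatment and 20,000 runs agrees: 67.5, 65.0 and 60.0% under the SAP rule at 5, 10 and 20% stopped, against 70.0% with last-score censoring.

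**Step 3, range.** Two further assumed curves have F(2), F(4), F(8), F(24) of 10, 20, 35, 55% and 25, 45, 65, 85%. Over all three curves and 5 to 30% stopped, the bias at 24 h is:
- stopping after 2 h: about −2.2 (0.05 × 45) to −18 points (0.30 × 60);
- stopping after 4 h: about −1.7 (0.05 × 35) to −12 points (0.30 × 40);
- stopping after 8 h: −1 (0.05 × 20) to −6 points (0.30 × 20).

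**Step 4, the median.** On the 70% curve with 20% stopped after 2 h, the 8 h estimate is 20 + 0.8 × 30 = 44% instead of 50%. The median moves from the 8 h to the 24 h entry.

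**Step 5, unequal stopping, no true effect.** With 5% stopped on LAT8881 and 20% on placebo (after 2 h), the difference is 67.5 − 60.0 = +7.5 points. With the rates swapped it is −7.5. Among 20 subjects, 7.5 points is 1.5 subjects.

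**Step 6, stopping because pain persists.** Assume 40% pain-free by 4 h, 76% by 24 h, and 20% of all subjects stopping after 4 h because their pain does not resolve. The SAP rule gives the true 76%. Last-score censoring leaves 60 − 20 = 40% at risk, of whom 36% have the event and 4% do not: 1 − 0.60 × (0.04/0.40) = 94%. With 10% stopping it gives 1 − 0.60 × (0.14/0.50) = 83%.

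**The case against.** The SAP sentence never mentions diaries that stop early. For a complete diary, the case it plainly covers, it is correct. It could also be read as applying only when a 24 h score was recorded and was above 1. That reading does not remove the problem: the SAP would then have no rule at all for a stopped diary, and the same sentence would be needed.

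Because the endpoint uses the primary endpoint's scores, the blinded review might impute those scores or exclude such subjects from the per-protocol set before the curve is drawn. Protocol 9.2 also checks diary compliance over at least 28 days of screening. Both may reduce the number of affected subjects. Neither sets a censoring time, and the imputation deferral covers the primary endpoint only.

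The strongest objection is Step 6. Last-score censoring needs stopping to be unrelated to outcome, and subjects may stop recording because pain persists. This stands: the replacement rule can be more biased than the present one, so it should not be adopted without a sensitivity analysis.

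A reader might infer that the SAP knowingly scores missing entries as pain, that the pain-free proportion is certain to be understated, or that the trial's treatment comparison is compromised. The documents support none of these. The first is a consequence of an unqualified rule and not a stated intention. The second depends on why diaries stop. The third overlooks that no primary or secondary result uses this curve.

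**Conclusion.** The point holds, at minor severity. As written, the rule gives a wrong Kaplan-Meier curve whenever a diary without a pain-free score ends before 24 h and the later outcome is unknown. The direction is conditional: the pain-free proportion is understated if stopping is unrelated to pain, and more so if subjects stop because they have become pain-free. If they stop because pain persists, the 24 h rule may be nearer the truth. The illustrated bias at 24 h runs from zero with complete diaries to −18 points in the most extreme case considered, and every rate behind it is assumed. The rule is not reliably conservative for the comparison, since unequal stopping can favour either treatment. What is affected is one exploratory, untested curve, its median and the descriptive comparison drawn from it.

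**What to change.** Replace the censoring sentence in SAP 10.15.5 with:

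> Subjects without a pain-free score are censored at the actual time of their last recorded NRS score, or at the 24 h entry if that was recorded.

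Using the actual time of the 24 h entry also puts censoring on the same clock as the events. At present an event recorded shortly after 24.0 h falls beyond the nominal censoring time.

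In addition:
- repeat the curve with all non-events censored at 24 h, as a sensitivity analysis;
- report the number of incomplete diaries by treatment;
- align 10.15.5 with the no-rescue condition in SAP 7.4, so that a score of 0 or 1 after rescue is not counted as an event, and state what time such a subject is given on the curve.

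The cost is a slightly longer derivation and one extra curve. No new data are needed, and the change should be made before unblinding.
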